#### 13.2.7.1 ECG Variables

ECG variables include heart rate, PR interval, RR interval, QRS interval, QT interval, and QTc intervals. QTc intervals include QTcB (Bazett's formula) and QTcF (Fridericia's formula). QTcF will also be categorized into the following categories (msec):

- Observed:  $\leq 450$ , 451 to 480, 481 to 500, and  $> 500$
- Change from Baseline:  $\leq 10$ , 11 to 30, 31 to 60, and  $> 60$

### 13.2.7.2 ECG Methods of Analysis

#### 13.2.7.2.1 Observed Values and Change from Baseline

Observed values and the changes from Baseline of ECG variables will be summarized using descriptive statistics at Baseline and all scheduled post-Baseline visits. The overall post-Baseline minimum, maximum, and last post-Baseline observed and change from Baseline values will also be summarized.

For the QTcF categorical analysis, the number and percentage of subject in each category will be summarized at each scheduled visit as well as overall post-Baseline maximum and last post-Baseline visit.

#### 13.2.7.2.2 PCI Values

Electrocardiogram values will be considered PCI if they meet or exceed the criteria listed in Table 6. The number and percentage of subjects with PCI values will be summarized at each scheduled post-Baseline visits and for overall post-Baseline.

For the by-visit summary, the numerator for the percentage is the number of subjects with a post-Baseline PCI value for the given parameter and visit, and the denominator is the number of subjects with non-missing values for the given parameter and visit.

For the overall post-Baseline summary, the numerator for the percentage is the number of subjects with at least 1 post-Baseline PCI value for the given parameter, and the denominator is the number of subjects with at least 1 post-Baseline value for the given parameter; all post-Baseline values will be considered, including unscheduled and out-of-window values.

A listing of all subjects with any PCI value will be provided for those parameters for which at least 1 PCI value was observed.

**Table 6 Criteria for Potentially Clinically Important ECG Values**

ECG Parameter	Unit	High PCI Criteria
QRS Interval	msec	$\geq 120$
PR Interval	msec	$\geq 220$
QTcB or QTcF	msec	$> 500$
QTcB or QTcF: change from baseline	msec	$> 60$

### 13.2.7.2.3 Cardiologist Interpretations

For cardiologist's interpretations, the number and percentage of subjects with ECG results that are determined as normal or abnormal will be summarized at scheduled visits. The overall post-baseline worst interpretation will also be summarized (i.e. if a subject has one or more ECG results that are considered as abnormal, this subject will be counted in the abnormal category). Cardiologist's interpretations will also be summarized in a shift table to determine the number and percentage of subjects with ECG results classified as normal or abnormal at scheduled post-Baseline visits relative to the same classification at the Baseline visit. The shifts from Baseline to overall post-Baseline worst interpretation will also be presented. For the by-visit shift summary, the denominator is the number of subjects with non-missing cardiologist's interpretation at Baseline and the given visit. For the summaries of shift from Baseline to the overall post-Baseline worst interpretation, the denominator is the number of subjects with non-missing Baseline and at least 1 post-Baseline cardiologist's interpretation.

### 13.2.8 Physical Examinations

A physical examination, including neurological examination (cranial nerves, motor, sensory, reflexes, gait, and coordination), will be performed at Screening and Week 16/ET visits.

Physical and neurological examination results (normal, abnormal, and not done) at Screening and Week 16/ET will be summarized in a frequency table by body system and visit. For purposes of the PCI analysis, any abnormal result will be considered as PCI.

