Exploratory Objectives To assess the extent to which caregivers and families experience additional demands, responsibilities, and difficulties To explore the effects of pimavanserin in subjects with PDP on: 
• Functional capacity• Cognition• Depressive symptoms• Nighttime behavior• Caregiver burden	Exploratory Endpoints 
• Change from Baseline to Week 16 on the Virtual Reality Functional Capacity Assessment Tool (VRFCAT) including total time to complete, total number of errors, and total number of forced progressions• Change from Baseline to Week 16 on the Caregiver Strain Index total score• Change from Baseline to Week 16 on the Neuropsychiatric Inventory-Questionnaire (NPI-Q) Nighttime Behavior Domain Severity and Caregiver Distress• Change from Baseline to Week 16 on the Geriatric Depression Scale (GDS) (Short Form)• Change from Baseline to Week 16 on mFSQ score by subscale
Safety Objective To assess the safety and tolerability of pimavanserin in adults with PDP	Safety Endpoints The safety and tolerability of pimavanserin will be assessed using the following: 
• Treatment-emergent adverse events (TEAEs)• Columbia-Suicide Severity Rating Scales (C-SSRS) score• Potentially clinically important (PCI) findings on:
• Physical examinations• Clinical laboratory tests• Vital signs• Electrocardiogram parameters
Number of Study Sites	Approximately 25 sites in the US will participate in this study.

Number of Subjects Planned	Approximately 89 subjects with PDP will be screened and 53 subjects are expected to be enrolled, assuming a screen failure rate of 40%. Approximately 42 subjects are expected to complete the study, assuming a 20% drop-out rate.
Test Product, Dose, and Administration	Pimavanserin 34 mg (provided as 1×34 mg capsule), administered orally, once daily

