4.2 Exclusion Criteria

A subject must meet none of the following exclusion criteria to be eligible for the study:

1. Has atypical parkinsonism (Parkinson's plus, multiple system atrophy [MSA], progressive supranuclear palsy [PSP]), or secondary parkinsonism variants such as tardive or medication induced parkinsonism
2. Has undergone ablative procedures such as a pallidotomy, thalamotomy, or treatment with focused ultrasound, or has an implanted deep brain stimulator
3. Is in hospice, is receiving end-of-life palliative care, or is bedridden or confined to a wheelchair
4. Has current evidence of an unstable neurological, cardiovascular, respiratory, gastrointestinal, renal, hepatic, hematologic, or other medical or psychiatric disorder, including cancer or malignancies that, in the judgment of the Investigator, would jeopardize the safe participation of the subject in the study or significantly interfere with the conduct or interpretation of the study
5. Has a history of epilepsy
6. Has atrial fibrillation unless adequately anticoagulated
7. Has a history of myocardial infarction, unstable angina, acute coronary syndrome, or cerebrovascular accident within the last 6 months prior to Screening
8. Has any of the following:
 - a. greater than New York Heart Association (NYHA) Class 2 congestive heart failure
 - b. Grade 2 or greater angina pectoris (by Canadian Cardiovascular Society Angina Grading Scale)
 - c. sustained ventricular tachycardia
 - d. ventricular fibrillation
 - e. torsades de pointes
 - f. syncope due to an arrhythmia
 - g. an implantable cardiac defibrillator
9. Glycosylated hemoglobin (HbA_{1c}) >8.5% at Screening
10. *This criterion has been deleted; please consult the Summary of Changes for details.*
11. Has a known history of a positive hepatitis B virus (HBV) or hepatitis C virus (HCV) test
12. Has a history of human immunodeficiency virus (HIV)

13. Has a history of neuroleptic malignant syndrome or serotonin syndrome
14. Has a known personal or family history of long QT syndrome or family history of sudden cardiac death
15. Has any of the following electrocardiogram (ECG) results at the Screening visit:
 - a. If the subject is not on citalopram, escitalopram, or venlafaxine:
 - i. QTcF >450 ms, if QRS duration <120 ms
 - ii. QTcF >470 ms, if QRS duration \geq 120 ms
 - b. If the subject is on citalopram, escitalopram, or venlafaxine:
 - iii. QTcF >425 ms, if QRS duration <120 ms
 - iv. QTcF >450 ms, if QRS duration \geq 120 ms

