### **2.4.1 Safety Endpoints**

The safety and tolerability of pimavanserin will be assessed using the following:

- Treatment-emergent adverse events (TEAEs)
- Columbia-Suicide Severity Rating Scales (C-SSRS) score
- Potentially clinically important (PCI) findings on:
  - Physical examinations

- Clinical laboratory tests
- Vital signs
- Electrocardiogram parameters

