### 3 STUDY DESIGN

#### 3.1 General Study Design

This study will be conducted as a 16-week, multi-center, single-arm, open-label study. Pimavanserin (ACP-103) will be administered at a dose of 34 mg to approximately 53 subjects with PDP. Approximately 42 subjects are expected to complete the study, assuming a 20% drop-out rate. Approximately 25 sites in the US will participate in this study.

The duration of participation for individual study subjects will be up to 26 weeks, consisting of the following 3 periods:

[figure not shown]
- Screening period (3-35 days)
- Treatment period (16 weeks)
- Safety follow-up period (30-34 days)

The study will be conducted on an outpatient basis with visits performed at Screening, Baseline (Week 0), Week 2, Week 4, Week 8, Week 12, Week 16 (end of Treatment Period) and Follow-up (at least 30 days and not to exceed 34 days after last dose of study drug). The first dose of study drug (pimavanserin) should be taken on the morning of the day after the Baseline visit.

The study start date is defined as the date the first subject is enrolled, which is the baseline visit date for the first subject. The primary completion date is the last date that subject data was collected for the primary outcome measure. The study completion date is defined as the last date that subject data was collected, which includes the safety follow-up telephone call visit.

[Figure 1](#) illustrates the study design.

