### **3.5 Determination of Sample Size**

This is an exploratory study and is not powered for statistical significance. Formal sample size calculations were not used to determine sample size.

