### 13.2.5.3 Potentially Clinically Important (PCI) Laboratory Values

The number and percentage of subjects with PCI laboratory values at scheduled post-Baseline visits Week 4 and Week 8 and overall post-Baseline will be summarized by Baseline status (all or within normal range) for selected parameters. PCI criteria are listed in [Table 3](#) and [Table 4](#). Subjects with multiple PCI values for a given parameter will be counted only once for that parameter. All post-Baseline values will be considered, including unscheduled and out-of-window values, for the overall post-Baseline visit.

For the by-visit summary, the numerator for the percentage is the number of subjects with a post-Baseline PCI value for the given parameter and visit, and the denominator is the number of subjects with non-missing values for the given parameter, and visit. For the overall post-Baseline summary, the numerator for the percentage is the number of subjects with at least 1 post-Baseline PCI value for the given parameter, and the denominator is the number of subjects with at least 1 post-Baseline value for the given parameter. For hemoglobin, hematocrit and uric acid, the count and percentage of subjects with PCI values will be presented for each gender as well as for both genders combined.

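### The physical-examination PCI rule in the SAP ignores Screening status, so in a Parkinson's population its rate will largely reflect pre-existing findings; Table 6 has a smaller version of the gap for QRS and PR only.

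*SAP*

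**What the plan says.** SAP 2.4.1 and Protocol 2.4.1 make PCI findings a safety endpoint with four components: physical examinations, laboratory tests, vital signs and ECG. The SAP treats the four differently.

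- **Physical examination (SAP 13.2.8).** Done at Screening and Week 16/ET, with a neurological part that includes motor function, gait and coordination. Results are normal, abnormal or not done, tabulated by body system and visit. Then: "For purposes of the PCI analysis, any abnormal result will be considered as PCI". No shift table is planned.
- **ECG (SAP 13.2.7.2.2, Table 6).** "Electrocardiogram values will be considered PCI if they meet or exceed the criteria listed in Table 6". QRS ≥120 ms, PR ≥220 ms and QTcB or QTcF >500 ms are absolute limits. The QTc >60 ms row is a change from Baseline. The overall count takes any subject with at least one post-Baseline PCI value.
- **Laboratory (SAP 13.2.5.3).** PCI counts "will be summarized by Baseline status (all or within normal range) for selected parameters". SAP 13.2.5.2 adds shift tables.
- **Vital signs (SAP Table 5).** Blood pressure and pulse need both an observed limit and a change from Baseline. Weight is change only.

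On entry status, Protocol 4.1 criterion 8 requires idiopathic Parkinson's disease with onset more than 1 year before Screening. Protocol 4.2 criterion 15 sets QTcF limits separately for QRS below 120 ms and for QRS of 120 ms or more, so the latter group can enter. No PR limit is listed.

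**The concern.** In a single-arm study, a safety rate is informative about treatment only if it can be separated from what subjects brought with them. The examination rule does not separate the two. A gait abnormality recorded at Screening and again at Week 16 counts the same as one that appeared on treatment. In this population, abnormal motor, gait or coordination findings at entry are to be expected.

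The two-visit frequency table does not repair this, because it shows totals and not who changed. Of the four PCI components, the examination is the only one with no planned within-subject comparison in its summaries.

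The schedule contains MDS-UPDRS Parts I and II but no clinician-rated motor part, so the neurological examination is the only scheduled motor examination done by a clinician. A PCI rate dominated by entry findings makes poor use of it.

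For ECG, a subject who enters with QRS at or above 120 ms and stays there is counted as a post-Baseline PCI case. The same holds for PR at or above 220 ms.

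**Working it through.** **Plan figures.** 89 screened × (1 − 0.40) = 53.4, stated as 53. 53 × (1 − 0.20) = 42.4, stated as 42 ("Approximately 42 subjects are expected to complete the study, assuming a 20% drop-out rate"). Both reproduce. The Week 16/ET denominator lies between 42 and 53, depending on how many early terminators are examined. The documents state no PCI rate and no share abnormal at entry.

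**Formulas.** Let N be subjects examined, p the share abnormal at entry, q the rate of new abnormality among those normal at entry, with no resolution. A subject is flagged if any result is abnormal.

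- Flagged under the present rule: N × [p + (1 − p)q]
- New abnormalities: N × (1 − p)q
- At risk of a new abnormality: N × (1 − p)

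All values of p and q are assumptions.

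**Physical examination, N = 42**

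| p | Flagged, q = 0 | Flagged, q = 10% | New, q = 10% | At risk |
|---|---|---|---|---|
| 50% | 21.0 | 23.1 (55%) | 2.1 | 21.0 |
| 80% | 33.6 | 34.4 (82%) | 0.8 | 8.4 |
| 90% | 37.8 | 38.2 (91%) | 0.4 | 4.2 |
| 95% | 39.9 | 40.1 (95.5%) | 0.2 | 2.1 |
| 100% | 42.0 | 42.0 (100%) | 0 | 0 |

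At p = 80%, for example: 42 × [0.80 + 0.20 × 0.10] = 34.4 flagged, of which 42 × 0.20 × 0.10 = 0.8 is new. The percentages are the same for N = 53. Raising q from 0 to 10% moves the rate by at most 2 percentage points once p is 80% or more. Even at p = 50%, half the subjects are flagged with nothing new.

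**What the by-visit table can show.** Suppose 38 of 42 are abnormal in a body system at both visits. Four were normal at Screening, so anything from 0 to 4 new abnormalities, offset by equally many resolutions, gives the same table.

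**QRS or PR, N = 42.** With p assumed at 5-20% and q = 0, 2.1 to 8.4 subjects are flagged. With q = 5%, 4.1 to 10.1 are flagged (10-24%), of whom 2.0 to 1.7 are new among 39.9 to 33.6 at risk. Here a Baseline split leaves most subjects at risk and separates old from new well.

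**QTc rows.** QTcF above 500 ms is above every entry limit in Protocol 4.2 criterion 15, and Protocol 6.3.5 discontinues a subject whose centrally read Baseline QTcF is out of range. The >60 ms row already refers to Baseline. Only QTcB >500 ms is not formally barred at entry.

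**The case against.** A reader might infer that both the examination and ECG rules flag nearly every subject and that neither can show a treatment-emergent change. The documents do not support this for ECG. Nothing in them ties Parkinson's disease to long QRS or PR, and two of the four Table 6 rows largely or wholly escape the objection. SAP 13.2.7.2.1 plans changes from Baseline for all ECG variables, SAP 13.2.7.1 gives QTcF change categories, and SAP 13.2.7.2.3 has a shift table of the cardiologist's interpretation. What remains is narrow: mean changes and an overall normal/abnormal shift do not count who newly crosses 120 ms or 220 ms.

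For the examination, the strong reading also goes too far. The table shows net change by body system, and systems unrelated to parkinsonism can stay informative. SAP section 5 lists all data, so about 53 subjects can be read individually. Protocol 7.1.1 leaves pre-existing conditions out of AEs only if they do not worsen, so new or worsened findings can appear as TEAEs. MDS-UPDRS Part II is analysed as change, in total and by item. Protocol 9.5.4.2 itself asks only for counts of abnormal examination findings. All of this stands, but none of it makes the examination PCI rate a treatment-emergent one.

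A further fair objection concerns the remedy. Replacing the rule with normal-to-abnormal alone would drop every subject already abnormal, however much that subject worsened. This also stands, and the all-abnormal count should therefore be kept alongside.

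Finally, the study is descriptive. No test, power figure or decision rule depends on these counts.

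**Conclusion.** The concern holds for the physical examination and, more narrowly, for QRS and PR. As written, the examination PCI rate combines entry status with new findings and will mainly reflect the former in the neurological components. Its size rests on an assumed entry rate: at 80-100% abnormal, about 34-42 of 42 completers are flagged with no new finding.

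For QRS and PR, an assumed 5-20% pre-existing rate gives about 2-8 of 42 flagged with no new event. That is a modest distortion in a component whose other summaries already refer to Baseline. The point is worth fixing because it affects a named safety endpoint and the SAP already uses Baseline status for laboratory and vital-sign PCI. It has no bearing on the efficacy analyses.

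**What to change.** 1. In SAP 13.2.8, add a Screening-to-Week 16/ET shift table by body system.
2. Report examination PCI two ways: all subjects with an abnormal result, as now, and subjects normal in that body system at Screening who are abnormal at Week 16/ET, with the number at risk as denominator.
3. In SAP 13.2.7.2.2, summarise QRS and PR PCI by Baseline status (all; not meeting the criterion at Baseline), following the laboratory approach.
4. State that worsening of an examination abnormality present at Screening is assessed from TEAEs.

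The cost is a few tables and some SAP wording, with no new data. The limitation is that few subjects will be at risk in the motor components (about 0-8 of 42 under the 80-100% assumption). Because results carry no grade beyond normal or abnormal, worsening there cannot be derived from the examination data.

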### 13.2.9 C-SSRS

The C-SSRS will be used to assess suicidal ideations and behaviors. The C-SSRS monitors changes in suicidal thinking and behavior over time, in order to determine risk. Four constructs are measured: the severity of ideation, the intensity of ideation, behavior, and lethality.

There are 5 questions about suicidal ideation, representing 5 types of suicidal ideation: wish to be dead; non-specific active suicidal thoughts; active suicidal ideation with any methods (not plan) without intent to act; active suicidal ideation with some intent to act, without specific plan; active suicidal ideation with specific plan and intent. If a subject answers "yes" to any of these 5 questions, that subject will be counted as having suicidal ideation.

The C-SSRS will be administered at Screening, Baseline, Weeks 2, 4, 8, 12 and 16/ET. The C-SSRS Baseline/Screening version will be used at the Screening visit, and the version assessing suicidality since the last visit will be used at all following visits (including the Baseline visit).

The event counts and the number and percentage of subjects reporting any post-Baseline suicidal ideation (wish to be dead; non-specific active suicidal thoughts; active suicidal ideation with any methods (not plan) without intent to act; active suicidal ideation with some intent to act, without specific plan; active suicidal ideation with specific plan and intent), suicidal behavior (preparatory acts or behavior; aborted attempt; interrupted attempt; actual attempt; suicide), or suicidality (any suicidal ideation or behavior) will be tabulated.

The event counts and the number and percentage of subjects reporting any post-Baseline non-suicidal self-injurious behavior will also be tabulated.

For calculating the percentages, the denominator will be the number of subjects with at least one post-Baseline C-SSRS.

## **14 CLINICAL PHARMACOKINETIC AND PHARMACODYNAMIC ANALYSES**

No pharmacokinetic samples are collected in this study.

## **15 INTERIM ANALYSIS**

An efficacy analysis may be performed when 50% of subjects have completed the study or terminated early. Additional analyses may be performed as necessary throughout the course of the study.

## **16 DATA MONITORING/REVIEW COMMITTEE**

There is no data monitoring/review committee for this open-label study.

## **17 COMPUTER METHODS**

Statistical analyses will be performed using Version 9.4 (or newer) of SAS® software on a suitably qualified and validated environment.

Validation and quality control of the tables, listings and figures containing the results of the statistical analyses will follow appropriate standard operating procedures.

## **18 CHANGES TO ANALYSES SPECIFIED IN PROTOCOL**

No changes are made to the analyses specified in the protocol.

## 20 APPENDICES

### 20.1 Summary of Version Changes

Version No:	Document History Description of Update	Author(s)	Version Date
1.0	Original version		01 March 2022

## 20.2 Schedule of Events and Assessments for ACP-103-063

Period	Screening	Treatment						Safety Follow-up
		Baseline						
Visit Week	-5 to 0	0	2	4	8	12	16/EOT	20 a
Visit Number	1	2	3	4	5	6	7/ET b	8
Visit window (days)			±3	±3	±3	±3	±3	+4
Type of Visit	clinic	clinic	clinic	clinic	clinic	clinic	clinic	telephone
Informed consent of subject	X							
Informed consent of caregiver or study partner	X							
Inclusion/exclusion criteria	X	X						
Medical history and demographics	X							
Weight, height, BMI	X	X					X	
Physical examination	X						X	
12-lead ECG c	X	X		X			X	
Vital signs d	X	X	X	X	X	X	X	
Clinical laboratory tests	X	X		X			X	
Urine drug screen	X							
Pregnancy test e	X	X		X	X	X	X	
MMSE	X							
C-SSRS	X	X	X	X	X	X	X	
FSQ	X	X		X	X	X	X	
Schwab & England ADL Scale (Patient)	X	X	X	X	X	X	X	
Schwab & England ADL Scale (Caregiver)	X	X	X	X	X	X	X	
NPI domains A and B	X	X						
NPI-Q Nighttime Behavior Domain only		X	X	X	X	X	X	

## 20.2 Schedule of Events and Assessments for ACP-103-063 (continued)

Period	Screening	Treatment						Safety Follow-up
		Baseline		16/EOT				
Visit Week	-5 to 0	0	2	4	8	12	16/EOT	20 a
Visit Number	1	2	3	4	5	6	7/ET b	8
Visit window (days)			±3	±3	±3	±3	±3	+4
Type of Visit	clinic	clinic	clinic	clinic	clinic	clinic	clinic	telephone
MDS-UPDRS Parts I and II (Patient)	X	X	X	X	X	X	X	
MDS-UPDRS Parts I and II (Caregiver)	X	X	X	X	X	X	X	
CGI-S specific to H&D	X	X	X	X	X	X	X	
CGI-I specific to H&D			X	X	X	X	X	
PGI-I specific to H&D			X	X	X	X	X	
VRFCAT	X	X		X			X	
Caregiver Strain Index	X	X	X	X	X	X	X	
Geriatric Depression Scale (Short Form)	X	X	X	X	X	X	X	
Concomitant medication	X	X	X	X	X	X	X	X
Assessment of adverse events		X	X	X	X	X	X	X
Dispense study drug		X	X	X	X	X		
Study drug return			X	X	X	X	X	
Study drug accountability			X	X	X	X	X	

Abbreviations: ADL=activities of daily living; BMI=body mass index; CGI-I=clinical global impression – improvement; CGI-S=clinical global impression – severity; C-SSRS=Columbia-Suicide Severity Rating Scale; ECG=electrocardiogram; EOT=end of trial; ET=early termination; FSQ= functional status questionnaire; H&D=hallucinations and delusions; MMSE=mini-mental state examination; NPI=neuropsychiatric inventory; NPI-Q=neuropsychiatric inventory – questionnaire; PGI-I=patient global impression – improvement; MDS-UPDRS=Movement Disorders Society – Unified Parkinson’s Disease Rating Scale; VRFCAT=virtual reality functional capacity assessment tool

a The safety follow-up telephone call visit is to occur 30 (+4) days after the last dose of study drug, nominally at Week 20 for completers and earlier for ET subjects.

b A subject terminating early should at a minimum complete assessments of safety (vital signs, ECG, AEs, clinical laboratories, C-SSRS) and, if possible, complete all Week 16 assessments.

- c The ECG may be repeated once at Screening in consultation with the Medical Monitor. ECGs can be performed any time before blood sampling or at least 30 minutes after blood sampling during clinic visits.
- d Vital signs (sitting or supine [ $>3$  minutes]) blood pressure, pulse rate, oral temperature, and respiratory rate) will be performed at Screening and each study visit.
- e Applicable only to women of childbearing potential. A serum pregnancy test is performed at Screening and a urine pregnancy test at Baseline and all subsequent visits (except Visit 3 at which neither serum nor urine pregnancy test is performed).
